AETC = AIDS Education and Training Center AIDS

= Acquired Immune Deficiency SyndromeART =

Antiretroviral Treatment

CAC = Cluster Auto-Correlation

CDC = Centers for Disease Control and Prevention

CDPH = Chicago Department of Health

Ce-PIM = Center for Prevention Intervention Methodology

CFAR = Center for AIDS Research

CFIR = Consolidated Framework for Implementation Research

DEBI = Diffusion of Effective Behavioral Interventions

EBI = Evidenced Based Interventions

EMR = Electronic Medical Record

GEE = Generalized Estimating Equation

GLM = Generalized Linear Model

HIPAA = Health Insurance Portability and Accountability Act

HIV = Human Immunodeficiency Virus

HRSA = Health Resources and Services Administration

ICC = Intra-Cluster Correlation

IS = Implementation Science

MATEC = Midwest AIDS Education Training Center

MIT = Massachusetts Institute of Technology

MPR = Medication Possession Ratio

MSM = Men Who Have Sex with Men

NHBS = National HIV Behavioral Surveillance System NIAID =

National Institute of Allergy and Infectious Diseases

NICHD = National Institute of Child Health and Human Development

NIDA = National Institute on Drug Abuse

NIH = National Institutes of Health

NIMH = National Institute of Mental Health

NIMHD = National Institute on Minority Health and Health Disparities

NINR = National Institute of Nursing Research

NUCATS = Northwestern University Clinical and Translational Sciences InstituteNUFSM =

Northwestern University, Feinberg School of Medicine

OR = Odds Ratio

PI = Principal Investigator

PID= Participant Identification

PWH = Persons with HIV

RCT = Randomized Control Trial

RE-AIM = Reach, Effectiveness, Adoption, Implementation, and Maintenance

SAMHSA = Substance Abuse and Mental Health Services Administration SES

= Socioeconomic Status

SD = Standard Deviation SMS

= Short Message ServiceUS =

United States

YLH = Youth Living with HIV

YYALH= Youth and Young Adults Living with HIV

YMSM = Young Men Who Have Sex with Men

PROTOCOL SUMMARY

In this study we propose to use implementation science (IS) to scale up and evaluate the TXTXT evidence-based intervention (EBI) as an effective strategy to increase ART adherence and retention in HIV care, ultimately leading to a suppression of viral load among Black/African American, Hispanic/Latino and other racial/ethnic minority youth and young adults living with HIV (YYALH) participating in the intervention. We hypothesize that those who complete the TXTXT intervention will demonstrate a clinically meaningful increase in ART adherence, viral suppression, and sustained retention in care. Additionally, we hypothesize that the implementation of TXTXT will reach $\geq 80\%$ of the intended participants, will be fully adopted by $\geq 80\%$ of clinic partners, and will achieve $\geq 90\%$ ratings of satisfaction and acceptability. We will use mixed methods to complete our study aims: 1) determine the real-world efficacy of a regional scale up of an EBI – TXTXT -among poorly adherent racial/ethnicity minority YYALH, aged 16-35 years, on our primary outcomes: adherence and viral load suppression at 3-month post initiation of the intervention; and secondary outcome: retention in HIV care at 12-months post baseline, and 2) apply the Consolidated Framework for Implementation Research (CFIR) to describe the implementation process and identify barriers and facilitators needed to be addressed; and measure implementation outcomes of the TXTXT intervention using the RE-AIM framework (Reach, Efficacy, Adoption, Implementation, Maintenance). We will conduct a cluster randomized controlled trial to evaluate the intervention effectiveness (i.e., ART adherence, viral load suppression) at 3-months post-initiation of the intervention. Twelve clinic sites with the ability to enroll up to 50 participants at each site (N=600 participants total) will be trained to administer the TXTXT intervention. Sites will be randomized to either start the intervention immediately (i.e., intervention arm) or waitlisted to start at 3 months post baseline (i.e., comparison arm). In the comparison arm, the study will compare pre-post differences in adherence and viral suppression at 6 months post baseline. Last, we will evaluate retention in HIV care and sustained impact of the intervention at 12 months post baseline for all study participants.

RESEARCH TEAM

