Project staff will inform participants that they have the right to skip any questions that make them feel uncomfortable. Participants will be informed that participation is completely voluntary and that they are free to stop their involvement in the study at any time without any negative consequences. Participants can stop their text messages by replying "STOP" at any time or by calling the participating clinic to unenroll in the study. Participants will be informed of their rights to privacy and confidentiality and will be told that their answers to the survey (collected via computer-assisted self-interview [CASI]) will be kept confidential and not shared with others outside of the research staff. They will be informed that no information about them or provided by them during the research will be disclosed to others without their written permission, except if necessary to protect their rights or welfare (for example, if they are injured and need emergency care) or if required by law (i.e., child or elder abuse, harm to self or others).

Dependent on site randomization, intervention sites will sign up eligible participants to receive automated SMS messages from the DimagiCommCare platform. Participants will have the option to tailor the message content based on their own preferences and will be able to select to receive messages in English or in Spanish. The time the messages are delivered, and frequency will also be selected. Clinic staff will use the text message tailoring form to record tailored messages (Appendix D). Clinic staff will enter information from this form into the text messaging platform, and then test receipt of text messages by the participant before they complete this first intervention visit. If the participant chooses a text message that discloses their HIV status, clinic staff will guide participants into selecting a discrete message and discuss options for alternate text. Participants at control sites will receive standard of care adherence counseling but will not enroll in text messaging until their site is eligible to receive the intervention. Messages used previously include, "Have you taken your vitamins

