Retention will be facilitated through obtaining contact information for the participant during the initial stages of the enrollment process. To minimize participant and staff burden, the follow-up visits can be conducted virtually. Participants will be sent a personalized link to complete the follow-up survey via REDCap. Of note, there will not be financial reimbursement for participation in the

intervention as the goal of the project is to understand how TXTXT will work in the “real world” and inform wide scale routine implementation. Prior studies by Drs. [name], [name], and [name] with vulnerable adolescent and other marginalized populations have maintained >80% retention. We will employ best practices in participant retention including: 1) collecting extensive locator information (multiple addresses/emails, phone numbers, social media profile names, etc.); 2) identification and discussion of difficult-to-reach participants and potential solutions during weekly team meetings; and 3) maintaining flexibility with mode of follow-up (e.g., in person options as well as internet based). The investigative team and participating clinic staff will review the study team’s retention plans and will be asked for guidance on how to best keep YYALH engaged in the study for at least 6 months. No financial incentives will be provided to youth participating in the TXTXT intervention trial (Aim 1). At 3 months, 6 months, and 12 months post baseline, electronic medical record (EMR) data from participating clinics will be used to determine viral load; retention in care will be assessed for up to 12 months post baseline.

STUDY DESIGN AND DATA ANALYSIS

Study participation summary

1. 12 participating clinics randomized 1:1 into intervention or comparison arm
2. 50 participants at each clinic enrolled and complete baseline survey; baseline EMR data pulled
3. Participants at intervention clinics begin TXTXT after baseline survey and continue for 6 months
4. All participants complete a 3-month survey
5. Participants at comparison clinics begin TXTXT after 3-month survey and continue for 3 months
6. All participants complete a 6-month survey; 6-month EMR data pulled
7. TXTXT intervention stops at 6 months post baseline for all participants
8. 12-month EMR data pulled

Timepoint	Who	What	Data collected
zero	12 participating clinics	Randomized 1:1 intervention: comparison arm	

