The data manager and study coordinator will review the Dimagi platform data reports, which include logs of all texts sent, received, responded to, as well as a log of “STOP” requests. These reports will be pulled by week and by clinic. The data manager and study coordinator will provide summary data to clinic sites as well as action items (e.g., follow up with “STOP” participants to inquire if they would like to discontinue from the study, or stop their messages for short time period). Summary statistics will be provided monthly as process data for the entire study team to review.

Sites in the control arm will continue the standard of care, which will include traditional adherence counseling. Data from the EMR will be gathered for both the control and intervention site participants to include viral load and visit attendance.

At baseline, univariate analyses will be used to characterize the sample; and bivariate analysis will be employed to explore any differences between groups (e.g., differences between clinics; age categories; sex). Fisher’s Exact Test and χ^2 tests (for categorical variables) and t-tests (for continuous variables) will be used to identify demographic and behavioral factors associated with adherence and retention in care. Generalized linear models (GLMs) will be used to assess the effect of the intervention on the outcomes between the intervention and the control arm at 3 months and pre-post differences in the control arm after received the intervention at 6 months. GLMs can accommodate dependent variables with normal, binary, Poisson, and negative binomial distributions and can be adapted to incorporate random and fixed effects (generalized linear mixed models; GLMMs) to account for within-subject correlation among repeated measures over time.³¹ The generalized estimating equation (GEE) can be used to compare ‘average’ population-level response to the intervention.³² Potential confounding and effect modification by sociodemographic characteristics and location (defined by urban vs. rural residence) will be examined in exploratory analysis and these variables will be selected for inclusion in multivariable models based on statistical significance and conceptual importance. All models will account for correlation among repeated measures on individuals and within sites over time as appropriate. Inclusion of random effects for intercept and trend over time will be explored to assess subject-specific variability.

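### The hypothesis is stated for completers, no analysis set is named, and the STOP follow-up opens a one-arm route out of the study before the 3-month primary outcome

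*Combined protocol and SAP*

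**What the plan says.** The effectiveness hypothesis in the Protocol Summary is that "those who complete the TXTXT intervention will demonstrate a clinically meaningful increase" in ART adherence, viral suppression and retention in care. Completion is not defined.

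The analysis text is about arms. In the Aim 1 Data Analysis Plan and Variables, generalised linear models assess the "effect of the intervention on the outcomes between the intervention and the control arm at 3 months". Aim 1 Research Design describes the same arm comparison. Neither section names an analysis set, and neither says how participants who stop the texts are to be analysed.

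On stopping texts, Procedures for Recruitment and Informed Consent (Aim 1, repeated under Aim 2) says that participants can do so by replying STOP "at any time or by calling the participating clinic to unenroll in the study". The Data Analysis Plan has STOP requests logged by week and clinic. As an example of an action item, sites follow up with STOP "participants to inquire if they would like to discontinue from the study, or stop their messages for short time period".

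On timing, control-site participants "will not enroll in text messaging until their site is eligible to receive the intervention", and the Study participation summary states: "Participants at comparison clinics begin TXTXT after 3-month survey and continue for 3 months".

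Adherence is a self-reported visual analogue score of at least 90% (Outcome definitions). Attrition is assumed to be 20%, leaving 480 of 600, with no split by arm. The Data and Safety Monitoring Plan says that missing data will be examined and gives no method for handling them.

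**The concern.** Completing the intervention, or stopping it, happens after randomisation, and before month 3 it has no counterpart in the comparison arm. A hypothesis about completers therefore concerns a population that randomisation did not create, and it differs from the population in the analysis text.

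The STOP procedure makes this a practical matter. The follow-up contact lists two choices: leave the study, or pause the messages for a short time. Someone who wants no more texts but would still answer surveys fits neither. Any participant who leaves at that contact before month 3 is from an intervention clinic and has no 3-month adherence value. If those who leave differ in adherence from those who stay, the arms are no longer comparable on the powered outcome, and the plan has no rule that would contain the effect.

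**Working it through.** **The passages side by side.**

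- Population: completers in the Protocol Summary; arms in Research Design and the Data Analysis Plan. Nothing reconciles the two.
- Schedule: intervention-clinic participants receive texts for 6 months and the primary comparison is at 3 months. If completing means the full course, nobody has completed at the primary time point.
- Access to STOP before month 3: intervention arm yes, comparison arm no. General withdrawal is open to both arms.
- Options listed at the STOP contact: leave the study, or pause. Ending texts with follow-up retained is absent.

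**The plan's own figures.** The concern does not make them wrong. With 40 analysed per site, two measures, within-site correlation 0.05 and within-participant correlation 0.2, the design effect is 1 + 2×39×0.05 + 1×0.2 = 5.1. Effective n per arm is 6×40×2/5.1 = 94.1. A two-sided 0.05 test of two proportions then gives power 0.826, 0.792, 0.792 and 0.826 for a 20-point difference at control rates of 25%, 35%, 45% and 55%. Table 2 has 0.82, 0.80, 0.80 and 0.83. Attrition also agrees: 480/(1 - 0.2) = 600.

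**Illustration of the bias.** The documents give no STOP rate and no adherence among those who stop, so these inputs are assumptions, apart from 35%, which is one of the plan's four control rates. Assume no true effect, adherence p = 0.35 in both arms, and extra loss s in the intervention arm only, with adherence q among those lost. The apparent difference is

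(p - s×q)/(1 - s) - p.

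| Extra loss s | Lost are half as adherent (q = 0.175) | None of the lost adherent (q = 0) | All of the lost adherent (q = 1) |
|---|---|---|---|
| 5% | 0.3592 - 0.35 = +0.9 points | 0.3684 - 0.35 = +1.8 points | 0.3158 - 0.35 = -3.4 points |
| 10% | 0.3694 - 0.35 = +1.9 points | 0.3889 - 0.35 = +3.9 points | 0.2778 - 0.35 = -7.2 points |
| 20% | 0.3938 - 0.35 = +4.4 points | 0.4375 - 0.35 = +8.75 points | 0.1875 - 0.35 = -16.25 points |

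**Effect on type I error.** This uses a normal approximation at the planned effective n of 94.1 per arm. For a spurious 5 points (0.35 against 0.40), the standard error is √[(0.2275 + 0.2400)/94.1] = 0.0705 and the shift is 0.05/0.0705 = 0.71. Two-sided rejection probability is Φ(0.71 - 1.96) + Φ(-0.71 - 1.96), about 0.11 instead of 0.05. The same calculation for 8.75 points gives about 0.23.

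**The case against.** The strongest reply is that the completer wording is one summary sentence. The operative text compares arms, the participation summary has all participants completing the 3-month survey, and the Protocol Summary evaluates all study participants at 12 months. A reader might infer that the trial will compare completers with all controls. The documents do not support that: no analysis section restricts to completers, and such a comparison does not fit a 3-month endpoint within a 6-month course.

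The STOP contact can also be read kindly. It offers a pause, it is only an example, and it may be meant to prevent STOP being taken as withdrawal. Appendix D tells staff to counsel participants that START resumes the texts, so STOP is reversible. The Retention section describes procedures to keep people in the study, and EMR data are gathered in both arms.

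These points reduce the risk without closing it. No passage says that follow-up continues after STOP or that such participants stay in the analysis. EMR data cannot supply self-reported adherence. For viral load at 3 months the schedule is itself inconsistent: Research Design and Retention promise EMR data then, while the participation summary and its table list only the survey.

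The objection about direction stands. People who take their medication reliably may stop because the reminders are unneeded or a nuisance; the acceptability survey in Appendix F asks about intrusiveness.

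**Conclusion.** The point holds as an unguarded risk of bias. The stated hypothesis and the analysis text refer to different populations, no analysis set is named, and the written STOP follow-up creates an exit route that exists in only one arm before the primary time point. Self-reported adherence is the exposed outcome.

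A reader might go further and infer that the arm comparison is biased in favour of the intervention by some 5 points. For example, with 45% adherent in both arms, 20% lost from the intervention arm only and 25% of those adherent, (0.45 - 0.2×0.25)/0.8 = 0.50, a quarter of the 20-point target. The documents do not support that as a finding. It puts 20% loss in one arm and none in the other, whereas the plan's 20% is overall attrition, and it assumes that those lost are less adherent. Under the assumptions in the table the bias runs from +0.9 to +4.4 points if those lost are half as adherent, reaches +8.75 if none are adherent, and is -3.4 to -16.25 if all are. At 5% to 10% extra loss with half-adherent leavers it is under 2 points. It should be corrected because the correction is cheap and suits the aim of real-world effectiveness, in which people who stop the texts are part of the answer.

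**What to change.** - Restate the hypothesis for all enrolled participants.
- Define the primary analysis as everyone enrolled, by the clinic's randomised arm, regardless of STOP or completion.
- Reword the STOP text in Procedures for Recruitment and Informed Consent (both aims) and the follow-up example in the Data Analysis Plan, so that STOP is recorded as the end of texts only. The 3- and 6-month surveys and consented EMR data continue unless research consent is withdrawn.
- Report STOP requests and loss to follow-up by arm.
- Pre-specify a sensitivity analysis for missing 3-month adherence, with those lost assumed both less and more adherent than those observed.
- Define completion and make any completer result secondary.

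The cost is protocol and SAP wording, a small amount of continued survey follow-up and one extra analysis. No change to sample size is needed.

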Black and Latino youth experience disproportionate rates of HIV compared to white youth. Accounting for only 14% of the US population, Black youth accounted for 51% of new HIV diagnoses in 2019, with Hispanic/Latino youth accounting for 30%.¹ Youth living with HIV (YLH) are also more likely to be racial/ethnic minorities. Young Black and Latino men who have sex with men (MSM) in the U.S. bear the disproportionate burden of HIV infection. HIV incidence is highest among young MSM (YMSM) aged 13-24 years, particularly Black and Latino YMSM.

Rates of infection among Black MSM are particularly relevant to the epidemiology of HIV in the Midwest, the region which has the second-highest rate of new HIV infections in Black residents, representing 47% of all new regional infections (Figure 1).¹ Despite the Midwest's relatively low national standing in terms of new diagnoses (only 7% of all new diagnoses of infections nationwide in 2019), there is an evident need for a more comprehensive approach to eliminating racial disparities in HIV infection in this region.¹ Rates of diagnoses in the Midwest decreased from 2015 to 2019 in addition to decreases in the South, Northeast, and West regions as well as 6 U.S. dependent areas (American Samoa, Guam, Northern Mariana Island, Puerto Rico, Republic of Palau, & U.S. Virgin Islands).¹ The Midwest region also contains several urban poverty areas sampled by the National HIV Behavioral Surveillance System (NHBS), including Chicago, Detroit, and St. Louis, which found very high prevalence rates of HIV among heterosexuals and an inverse relationship between HIV prevalence rates and socioeconomic status (SES).²

In addition to disproportionate risk for HIV infection, MSM and other YLH are less likely to be adherent to antiretroviral therapy (ART).³ Low adherence is problematic because ART suppresses viral load and results in better long-term health.⁴ A secondary benefit of viral suppression is that it prevents onward transmission, as people who are virally suppressed are extremely unlikely to transmit HIV.⁵

[figure not shown]
The effort to identify individuals with HIV infection, link and keep them engaged in care, support adherence to ART and suppress viral replication is known as the “HIV care continuum”.⁶ This project focuses on adherence to ART, a step in the HIV care continuum that has not been prioritized among youth and young adults to the same degree as earlier steps in the continuum. Correlates of ART adherence among youth include key psychosocial factors, such as co-morbid mental illness, substance use and HIV-related stigma, among

other factors.⁷ Youth and young adults living with HIV (YYALH) are more likely to disengage from care, delay initiation of ART, and have lower rates of virologic suppression compared to adult populations.⁸⁻¹⁶

However, the most frequently cited reason for non-adherence among YLH is simply forgetting. In a study of youth living with HIV, (aged 12-24 years; n=217), 74% reported the reason for missing doses was that they “forgot”.¹⁷ These findings underscore the need for implementation of reminder interventions, including novel and proven effective intervention strategies such as the TXTXT intervention described herein.

The TXTXT intervention¹⁸ will be adapted, pilot-tested, and scaled up in this project (Appendix A-
<https://www.cdc.gov/hiv/pdf/research/interventionresearch/compendium/ma/cdc-hiv-text-messaging-txtxt-good-ma.pdf>). TXTXT uses a two-way daily text reminder and response system designed by [name] and colleagues, to improve ART adherence for 16-29 years old U.S. adolescents and young adults.¹⁸ Both HRSA and the CDC have designated TXTXT as an effective HIV treatment intervention for ART adherence.¹⁹ While the original TXTXT intervention focused exclusively on ART adherence, for the purposes of the proposed study, we will adapt the intervention to deliver SMS text reminders not only for ART adherence, but also to focus on critical aspects of retention in care (e.g., clinic appointment and pharmacy refill reminders) as our primary outcome; viral suppression, is influenced by both. Further, we have expanded the age range up to 35 years to include young adults who often struggle with adherence as they transition into adulthood and face other developmental milestones.

Figure 1. Diagnoses of HIV infection among men who have sex with men by region and race (United States 2019)

Given the potential to accelerate progress towards no new HIV infections, the United States is at a critical point in the epidemic to support persons with HIV (PWH), particularly racial/ethnic minority youth, in achieving and sustaining viral suppression.²⁰ Deaths among PWH have decreased, resulting in an increasing prevalence; therefore, disparities in ART adherence in racial/ethnic minority youth must be the continued focus of these efforts in order to promote viral suppression and prevent onward transmission.^{16,18,21,22} Evidence-based interventions for these youth across the HIV care continuum should be scaled up and widely disseminated to increase access to effective strategies.

The proposed implementation science research project “Midwest TXTXT” will focus on the Ending the HIV Epidemic Initiative *Treating people with HIV rapidly and effectively to reach sustained viral suppression* by delivering an evidence-based intervention to improve ART adherence, retention in care and sustained viral suppression among racial/ethnic minority youth, inclusive of young gay, bisexual and other MSM, young cisgender women and young transgender women across multiple sites.²⁰

Justification of the Study

The goal of the proposed project is to implement a scaled-up version of the existing TXTXT EBI in an effort to increase the rate of viral suppression among YYALH aged 16-35 years through medication adherence and retention in HIV medical care. In addition to disproportionate risk for HIV infection, racial and ethnic minority YYALH are less likely to be adherent to antiretroviral therapy (ART).³ The most frequently cited reason for non-adherence among YYALH is simply forgetting.¹⁷ The results of this study, if the adapted intervention proves to be an impactful and acceptable innovation, will be used to scale up this intervention further so that it can be used as a practical and sustainable tool at the regional level within clinic settings in the United States.

Innovation

This study is innovative for the following reasons:

1. **Scale-up and adaptation of a medication adherence intervention developed specifically for YYALH, only one of two such EBIs in the CDC Compendium:** In addition to the TXTXT intervention there is only one other intervention in the CDC Compendium that has been developed for youth, adolescents, or young adults (Red Carpet program). See <https://www.cdc.gov/hiv/research/interventionresearch/compendium/index.html> Of note, the Red Carpet program is a structural intervention that was evaluated in an international setting for YLH and consisted of fast tracked peer navigation to support linkage to and retention in care.
2. **Leverage of collaboration with a systems-level HIV/AIDS service partner, MATEC, to promote medication adherence among racial/ethnic minority youth, who have the lowest rates of viral suppression:** This widespread implementation of an EBI in conjunction with an already existing HIV service infrastructure is a novel approach to HIV care.

3. **Systems-level Implementation Science Approach:** Implementing this EBI at the systems-level or regional scale with MATEC has the possibility of broadening the reach of such an intervention.
4. **Targeting a diverse set of clinics who partner with MATEC across the Midwest region who serve Black and Latinx youth with poor adherence:** This initiative will allow us to test the intervention throughout MATEC's network of clinics but also allow us to compare different types of clinics within the network (i.e., Ryan White Care Act clinics versus non-Care Act clinics).

Conceptual Framework

Implementation Science

Implementation Science is a critical new area of HIV prevention and intervention science which provides the frameworks and methods to effectively translate evidence to practice in the next era of HIV prevention intervention for public health impact.²³ As articulated by the CDC, a set of lessons learned from 20 years of diffusion of effective behavioral interventions (DEBI) and EBI projects will influence the next wave of dissemination and intervention initiatives. Implementation Science (IS) frameworks and methods provide the tools to incorporate these lessons into IS initiatives.²³ Furthermore, IS approaches allow us to measure systems-level HIV intervention implementation, a promising, but much rarer form of implementation.²⁴ By systematically studying the factors that influence implementation at higher levels of implementation, as well as evaluating specific implementation outcomes, we can shift our focus from intervention efficacy to public health impact among those populations most affected by the epidemic, including racial/ethnic minority youth.

IS approaches are necessary to understand and inform the roll out and scale up of effective strategies to increase ART adherence. IS studies have highlighted the need for multilevel interventions and diverse models of dissemination. Implementation science also provides relevant conceptual and measurement frameworks to guide a hybrid trial of clinical outcomes and implementation factors.²⁵⁻²⁸

The Reach, Effectiveness, Adoption, Implementation, and Maintenance (RE-AIM) framework is an evaluation and reporting scheme commonly used to examine the potential public health impact of an intervention.²⁹ Reach represents the number and representativeness of patients who participate out of the eligible patient population. Effectiveness is the impact of the intervention on participant outcomes.

Adoption is the number and representativeness of eligible staff/settings that agree to deliver the intervention out of all eligible staff/settings. Implementation is the fidelity to the intervention. Maintenance is the degree to which the intervention is sustained over time. RE-AIM provides a useful measurement framework for capturing both clinical and implementation outcomes within the same study.

Implementation science also provides relevant conceptual and measurement frameworks to guide an assessment of factors which influence implementation outcomes. We will use the Consolidated Framework for Implementation Research (CFIR), which has been used to guide the implementation and evaluation of numerous evidence-based health programs, synthesizes the concepts of several available models into five inter-related domains: intervention characteristics, outer setting, inner setting, characteristics of individuals involved, and the process of implementation, with several constructs in each domain.²⁵ CFIR accounts for the non-linear process of implementation and incorporates consideration of the adaptation that is required for different context.

Theoretical Framework of TXTXT Intervention

TXTXT uses a two-way daily text reminder and response system designed by the mentor of the current PI, [name], to improve ART adherence for 16-29 years old U.S. adolescents and young adults.¹⁸ Both HRSA and the CDC have designated TXTXT as an effective HIV treatment intervention for ART adherence (Appendix A-Text Messaging TXTXT (cdc.gov)). TXTXT is a theory-based intervention that is grounded in social cognitive theory. Social cognitive theory specifies a core set of factors and mechanisms that influence health behavior with a primary emphasis on self-regulation (i.e., the accuracy and consistency of self-observation and self-monitoring) and self-reflection, including self-efficacy.³⁰ Social cognitive theory holds that cognition, behavior, and environmental influences interact and are reinforcing. Self-regulatory functions, for example, are enhanced by facilitative environmental conditions, such as reminder systems. A key developmental task for youth living with HIV is to take responsibility for management of their health care. Text messages are a supporting external influence, which is expected to enhance self-regulation, specifically the feeling of control over one's ability to take medications as prescribed. Self-efficacy is the foundation of motivation and action. Receipt of text messages is expected to help overcome a key barrier to adherence, forgetting to take medication, which may increase self-efficacy and thus, motivation. Among youth living with HIV, motivation and self-efficacy are strongly related to adherence; a relationship which is likely to be mutually reinforcing.

STUDY OBJECTIVES

There are two specific aims for this research:

Aim 1

Determine the real-world effectiveness of a regional scale up of an EBI- TXTXT- among poorly adherent racial/ethnic minority YYALH, aged 16-35 years on our primary outcomes: adherence and viral load suppression at 3-month post initiation of the intervention; and secondary outcome: retention in HIV care, at 12-months post baseline.

Aim 2

Apply the Consolidated Framework for Implementation Research (CFIR) to describe the implementation process and identify barriers and facilitators needed to be addressed; and measure implementation outcomes of the TXTXT intervention using the RE-AIM framework (Reach, Efficacy, Adoption, Implementation, Maintenance).

AIM 1: RESEARCH QUESTION AND OBJECTIVES

Aim 1: Determine the real-world effectiveness of a regional scale up of an EBI- TXTXT- among poorly adherent racial/ethnic minority YYALH, aged 16-35 years on our primary outcomes: adherence and viral load suppression at 3 months post initiation of the intervention; and secondary outcome: retention in HIV care at 12 months post baseline.

RESEARCH DESIGN

The proposed research uses a cluster randomized controlled trial design to evaluate the effectiveness of TXTXT intervention on adherence and viral load suppression at 3 months post intervention initiation. A total of 12 clinic sites in the Midwest will be randomly assigned to either a 3- month observation period (i.e., comparison arm) or a 3-month intervention period (i.e., intervention arm). At the 3-month mark, sites randomized to the intervention arm will continue with the intervention for an additional 3 months, and sites initially assigned to the comparison arm will switch to the intervention for the 3 months. We will assess initial impact of the intervention by comparing the primary outcomes (i.e., ART adherence and viral load suppression) of the intervention arm to the comparison arm at 3-months post initiation of the intervention. This timepoint (3 months post baseline) was selected based on the findings of the randomized control trial used to establish efficacy of TXTXT.¹⁸ The study will also compare pre-post differences in adherence and viral load suppression for participants in the comparison arm at 6 months post baseline. Secondary outcomes of retention in HIV care and sustained impact of the intervention will be evaluated at 12 months post-baseline. At 3 months, 6 months, and 12 months post baseline, electronic medical record (EMR) data from participating clinics will be used to determine viral load and retention in care measures.

METHODS

Audience and Stakeholder Participation

The Midwest AIDS Training and Education Center (MATEC) is the ideal partner and stakeholder for us to carry out the proposed project. The partnership with MATEC will not only ensure the feasibility of this project but will also serve as a valuable partner in future work to increase dissemination of effective interventions throughout the Midwest and via strategic connections to the larger AIDS Training and Education Center (AETC) network. MATEC has a 32-year history as an AETC covering 7 jurisdictions across a 10-state region and oversees 8 different federally funded projects in the Midwest. Further, MATEC leads a practice transformation cohort consisting of 13 Ryan White funded clinics with the goal of advancing plans to End the Epidemic by increasing testing, identification of PWH, linkage to and retention in HIV care, and increasing viral suppression. We sought collaboration with MATEC specifically for this project because they are a regional hub for capacity development among HIV/AIDS service providers in the Midwest.

Study Population

Poorly adherent racial/ethnic minority youth living with HIV aged 16-35 years inclusive of all gender and sexual identities and orientations, including young gay, bisexual and other MSM, young cisgender women and young transgender women across multiple clinic sites in the Midwest US.

Inclusion and Exclusion Criteria

Clinic site inclusion criteria

MATEC affiliated clinics in the Midwest region are eligible to participate in Aim 1 if meeting these criteria: (1) Clinic must have at minimum 40 current patients who are: racial/ethnic minority AND have a 'detectable' viral load AND are aged 16-35 years; (2) clinic must be willing to commit at least one staff person as lead for registering clients to receive the intervention, completing consent, and administering research surveys; (3) clinic must be willing to provide deidentified individual-level data for registered TXTXT participants, including viral load, retention in care (dates of clinic visits) at least twice per year; (4) clinic must not be using a competing medication reminder text messaging system; (5) clinic must be willing and able to rely on Lurie IRB. Once sites sign a memorandum of commitment, the study coordinator will schedule a conference call to conduct a standard of care questionnaire (Appendix K). The standard of care questionnaire will document existing clinic approaches to support adherence as well as any ancillary services (e.g., transportation assistance). This information will form a descriptive profile for each clinic.

Study Inclusion

For inclusion in the TXTXT intervention individuals must meet the following criteria: 1) diagnosed with HIV-infection and on ART regimen for at least one month (not new to ART); 2) aged 16-35 years; 3) have a viral load ≥ 200 c/mL and/or report poor adherence (<90% of pills taken in the last 30 days); 4) able to receive text messages; 5) provide informed consent for research component; and 6) are a patient of a participating clinic

Study Exclusion

Exclusion criteria includes: 1) those who are unable to give informed consent 2) those who are participating in other studies that impact primary and secondary outcomes.

Procedures for Recruitment and Informed Consent

Aim 1: Youth living with HIV (aged 16-35 years) who meet study inclusion criteria will be recruited by study staff from participating clinics. The EMR will identify potentially eligible patients who will be invited to complete further study screening and enrollment.

We will ask each clinic to construct a list of eligible patients and carefully track outreach, screening, and enrollment on an enrollment log provided. Clinics may enroll up to 50 participants (to account for 20% attrition, final sample of 40 participants per clinic).

